2. HYPOTHESIS

We hypothesize that the use of serratus plane blocks for ambulatory breast surgery postoperative analgesia will provide improved pain relief while resulting in decreased opioid usage and opioid-related adverse events such as nausea and vomiting, thus improving patient recovery and satisfaction.

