3. Prior to surgery, upon receipt of physician's orders, the randomization system will be accessed by the pharmacist and the treatment and randomization/subject ID number will be obtained. The syringe will be prepared and the randomization/subject ID number will be confirmed to match the randomization system by a 2nd member of the pharmacy staff.
4. This syringe (prepared upon receipt of physician's orders) will be collected from pharmacy and brought to the OR.
5. For patients enrolled in the investigational arm of the study, prior to surgery, following induction of general anesthesia, serratus plane block (**20mL bolus of drug, 0.25% of bupivacaine HCl will be administered underneath the fascia of the serratus muscle for each subject using ultrasound guidance**) will be performed on the operated side(s) (See section "Investigational Study Group" for further details).
6. For patients enrolled in the control arm of the study, prior to surgery, a placebo injection of normal saline will be performed on the operated side(s) using the same technique as the serratus plane block with bupivacaine (**0.9% saline administered underneath the fascia of the serratus muscle for each subject using ultrasound guidance**).

e. Investigational Study Group

1. In the operating room before surgery, patients enrolled in the investigational study group will receive an injection of bupivacaine as a serratus plane block on the operated side(s) in the standard fashion.
2. After the surgery is complete, patients will be awoken from general anesthesia, extubated, and transferred to the PACU.
3. Patients will receive oral standard post-operative pain and nausea management on an as-needed basis in the PACU.

f. Control Study Group

1. For patients enrolled in the control study group, the procedure takes place in the usual fashion. Patients in this group undergo a placebo injection of normal saline on the operated side(s) at the same time, using the same technique as the serratus plane block.
2. After the procedure is complete, patients will be awoken from general anesthesia, extubated, and transferred to the PACU.
3. Patients will receive oral standard post-operative pain and nausea management on an as-needed basis in the PACU.

g. Data Collection:

In addition to basic demographic information, the patients post-operative course will be reviewed.

Information to be collected:

1. Medical record number;
2. Date of surgery;
3. Type of Surgery
4. Race/Ethnicity

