5. Length of PACU stay (hours);
6. Age at time of surgery (years);
7. Height (cm);
8. Weight (kg);
9. Body mass index (kg/m²);
10. Indication for procedure;
11. Surgical procedure(s) performed;
12. Attending breast surgeon (for patients having concurrent breast surgery)
13. Attending plastic surgeon
14. Length of procedure (hours);
15. Perioperative intravenous administration (including dose) of fentanyl, Tylenol, and Toradol;
16. Postoperative intravenous administration (including total dose) of morphine, dilaudid, Tylenol, toradol, and other analgesic agents;
17. Postoperative oral administration (including total dose) of Percocet, morphine, dilaudid, Tylenol, Toradol, and other analgesic agents;
18. Postoperative oral and IV use of antiemetics (Zofran, etc).
19. Self-reported pain score using the 0–10 Numeric Pain Rating Scale.
20. Self-reported nausea score using the 0–10 Numeric Pain Rating Scale.
21. Vomiting episodes
22. Past medical history including diabetes mellitus, history of neuropathy (of any etiology), history of seizures, pre-existing pain conditions, and regular (defined as use > 3 times weekly) analgesic use (including type of analgesic used), allergies or adverse reactions to NSAIDs or opiates;

The study will collect pain and nausea scores in the PACU every 30 minutes up to 4 hrs and at 1 hr intervals after 4 hours for the duration of PACU stay. With respect to timing of collection of scores, time zero will be PACU admission and all time intervals for pain score assessment will be determined using this time as a reference. Investigators will also follow up within one week of surgery to determine patient satisfaction and collect pain scores documented by patients following discharge.

h. Endpoints:

1. ***Amount of narcotic administered(morphine milligram equivalents).***

The primary endpoint will be narcotic usage for the first 4 postoperative hours. Postoperatively, oral and IV rescue medication will be administered to both groups upon request as per standard of care. The use of narcotics will also be recorded intra-operatively, for the duration of PACU and hospital stay and up until the end of postoperative day one. Consumption of rescue medication will be converted to the morphine equivalent (ME) dose for analysis. Analysis will be performed on both groups to allow comparison of effect of block with placebo and bupivacaine on total opioid consumption.

2. ***Postoperative Pain.***

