Postoperatively, pain intensities at rest and on movement will be assessed every 30 minutes in the PACU for the first four hours and at hourly intervals up until PACU discharge, using the visual analog scale (VAS) with two anchor points; 0 being no pain and 10 being the worst pain imaginable. Following discharge patients will be asked to record their pain upon and one hour after taking their pain medication up until the end of the first postoperative day.

3. ***Postoperative Nausea (Incidence and rating).***

Evaluation will be performed at every 30 minutes in the PACU for the first four hours and at hourly intervals up until PACU discharge using a standard 11-point verbal rating scale, for which “0” represents “no nausea” and 10 represents “worst nausea imaginable.” Significant nausea is defined as a score of ≥ 4 .

4. ***Vomiting.***

This will be recorded throughout PACU stay until discharge. Vomiting will be measured as the number of emetic and retching (recorded separately) episodes occurring at least 1 minute apart during entire PACU stay. Severe vomiting will be defined as 3 or more episodes during a given time interval. Vomiting and retching episodes will be counted as necessary up to PACU discharge.

5. ***Amount of antiemetic administered.***

Amount of antiemetic administered intra-operatively, during PACU and hospital stay will be recorded.

6. ***PACU Length of Stay.***

7. ***Patient Experience and Satisfaction.***

Patient satisfaction with postoperative pain and and overall patient satisfaction with their surgical experience will be assessed within one week following discharge with a follow up phone call using a 5-point categorical scale.

i. Statistical Considerations

1. **Brief Summary:** This is a double blind randomized, placebo controlled trial of Bupivacaine vs Placebo for the treatment of post-op pain following outpatient breast surgery.
2. **Primary Endpoint:** Narcotics usage (IV or PO) for first 4 hours in the PACU, expressed as morphine equivalents (ME) .
3. **Secondary Endpoints:** Narcotic usage for the duration of PACU and hospital stay and up to postoperative day one, antiemetic administration in PACU (no, yes); PACU length of stay, Self-reported pain using the 0–10 Numeric Pain Rating Scale during the first 4 hours of PACU stay, hospital stay and up until the end of the first postoperative day. Self-reported nausea, vomiting episodes during PACU stay and patient satisfaction with pain management.

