4. **Statistical Methods:**

Primary - Analysis of covariance (ANCOVA) with “type of surgery” as a covariate will be used to compare mean ME between the two groups. (The inclusion of these covariates in the model is in accordance with ICH E9 Section 5.7 guidelines.) Data transformation (presumably a log transform) will be considered in order to achieve the required assumptions of normality and equal variance.

Secondary – The chi-square test will be used to compare anti-emetic rates and patient satisfaction. ANCOVA will be used to compare LOS, pain and nausea scores.

5. **Intention to Treat (ITT):** The ITT population will be defined as all subjects who are randomized. All primary analyses will be carried out on the ITT population.
6. **Sample Size Considerations:** A two-sample t-test approach is used as a reasonable simplification of the ANCOVA method. Based on previous data, it is expected that the Placebo group will average 12 ME (SD=4) of narcotics in the PACU. A reduction of 20% to 9.6 ME in the Bipuvacaine group would be clinically significant. A sample size of n=45 subjects per group (total 90) will yield 80% power to detect such a reduction (alpha=0.05, 2-tailed t-test).
7. **Interim Analysis:** There will be no interim analysis for early stopping of the trial.

j. Adverse events

An adverse event (AE) is any untoward medical occurrence in a clinical investigation of a patient administered a pharmaceutical product and that does not necessarily have a causal relationship with the treatment. An AE therefore is any unfavorable and unintended sign (including an abnormal laboratory finding), symptom or disease temporally associated with the administration of an investigational product, whether or not related to the investigational product. An unexpected AE is one of a type not identified in nature,

severity, or frequency in the study protocol or of greater severity or frequency than expected based on the information in the study protocol.

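### After discharge, pain is scored only around doses of pain medication, so the home part of the secondary pain endpoint compares patients and moments selected after randomisation

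*Combined protocol and SAP*

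**What the plan says.** In the PACU, pain is scored on a clock: half-hourly for four hours, then hourly until discharge (9.g, 9.h.2). At home the trigger changes to dosing: "Following discharge patients will be asked to record their pain upon and one hour after taking their pain medication", continuing to the end of postoperative day one. The follow-up contact described in 9.g will only "collect pain scores documented by patients following discharge". No other home pain assessment appears.

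These scores feed a listed endpoint. Section 9.i.3 makes self-reported pain a secondary endpoint over the first four PACU hours, "hospital stay and up until the end of the first postoperative day". Section 9.i.4 then says "ANCOVA will be used to compare LOS, pain and nausea scores". It names no summary measure or window for pain, and gives no rule for patients without a home score or with unequal numbers of scores. The intention-to-treat statement in 9.i.5 covers primary analyses only.

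The hypothesis in section 2 is "improved pain relief while resulting in decreased opioid usage". On how medication is taken, 9.e and 9.f describe "oral standard post-operative pain and nausea management on an as-needed basis in the PACU", and 9.h.1 says "oral and IV rescue medication will be administered to both groups upon request as per standard of care". Neither states the dosing basis at home.

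**The concern.** Whether a home score exists, and at what moment, depends on the patient taking pain medication after randomisation. If the block changes that behaviour, the two arms contribute differently selected patients and differently selected hours, and randomisation no longer protects the comparison. A patient comfortable enough to take nothing, arguably the best result, contributes no home pain data.

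At stake is the reading of one component of one secondary endpoint. A difference in home scores, or its absence, could not be taken as the effect of the block on pain after discharge. Because surgery is outpatient, much of the window to the end of day one is likely to be spent at home. Scores that were never recorded cannot be recovered at analysis.

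**Working it through.** **The plan's own figure.** The documents give no figures for home pain. Their one computable figure is the primary sample size: difference 12 − 9.6 = 2.4 ME, SD 4, 45 per arm. The noncentrality is 2.4 / (4 × √(2/45)) = 2.85, which gives 80.4% power by the two-sample t-test. The stated 80% reproduces; this point does not depend on it.

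**Structure.** Setting 9.h.2 beside 9.g and 9.i.3 is enough for the main conclusion: scores exist only around doses, only those scores are collected, and they form part of a compared endpoint. This step needs no arithmetic.

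**Size and direction.** These need assumptions, none of them from the documents except 45 per arm and ANCOVA with three surgery types:

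- Hourly pain over 24 h on a 0–10 scale; placebo mean 4; between- and within-patient SD 1.5.
- Benefit of 1 point, the same for every patient and constant over 24 h unless stated.
- A dose is taken when pain reaches a threshold of 3, 4 or 5, at most once per 4 h (a modelling device only). Analgesia lowers scores for 4 h.
- The dose-linked measure is the per-patient mean of the at-dose and one-hour scores. The comparator is mean observed pain over all hours, with medication use included. Fixed scores are taken at hours 3, 11, 16 and 21.

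Patients with no home score at thresholds 3/4/5: 4%/13%/30% on block against 1%/4%/13% on placebo. At threshold 4 that is about 0.13 × 45 = 6 against 0.04 × 45 = 2 patients.

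Placebo-minus-block differences at thresholds 3/4/5:

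| Scenario | All hours | Dose-linked |
|---|---|---|
| Same benefit for all, 2-point analgesia | 0.67/0.65/0.65 | 0.50/0.45/0.37 |
| Same benefit for all, 3-point analgesia | 0.54/0.50/0.51 | 0.44/0.39/0.33 |
| 2-point benefit only if usual pain is below 4, 2-point analgesia | 0.47/0.52/0.64 | 0.18/−0.07/−0.28 |
| 2-point benefit only if usual pain is 4 or more, 2-point analgesia | 0.75/0.68/0.62 | 0.61/0.60/0.57 |
| Scheduled 6-hourly dosing, same benefit for all, 2-point analgesia | 0.84 | 0.87 |

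In the first row the dose-linked difference is 0.50/0.67 = 75%, 0.45/0.65 = 69% and 0.37/0.65 = 57% of the all-hours one. With 3-point analgesia, threshold 5 and benefit only at usual pain of 4 or more, the bias is slightly upward (0.52 against 0.46). In a simpler model where dosing depends only weakly on pain, the difference in at-dose scores is nearly intact (0.92 against 0.95).

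**Fixed-time scores.** With the same constant benefit for all, four fixed scores give 0.66/0.62/0.63 (2-point analgesia) and 0.51/0.48/0.48 (3-point), within about 0.03 of the all-hours values. That closeness needs a benefit that lasts the whole window. If a 2-point benefit wanes to zero by hour 12 (2-point analgesia), fixed scores give about 0.24–0.27 against 0.35–0.37 over all hours. Dose-linked scores are further off, at about 0.12–0.21; at threshold 5 the result varies with the run and can be as low as 0.08.

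The reason is timing. With a linear decline, the nominal benefit averages 13/24 = 0.54 over the hours, but (1.5 + 0.17 + 0 + 0)/4 = 0.42 at hours 3, 11, 16 and 21.

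**Power at thresholds 3/4/5, constant benefit, fixed against dose-linked.** 2-point analgesia: 69/66/66% against 77/64/43%. 3-point analgesia: 52/47/47% against 74/63/39%.

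**The case against.** The strongest reply has four parts.

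First, the hypothesis concerns opioids, while any pain medication triggers a score, and 9.g lists Tylenol and Toradol among the oral agents. A reader might infer that the trial expects less use of all pain medication, and hence many unscored block patients. The documents do not say so: a patient who replaces an opioid with a non-opioid still gives scores. This stands. The block may change whether and when doses are taken, but the no-score percentages come only from assumed inputs.

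Second, a reader might infer that the bias is toward no difference. That needs as-needed dosing at home and a similar benefit across patients, and neither is documented. The as-needed statement covers the PACU. This stands too, and the direction is only conditional.

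Third, narcotic use to postoperative day one is already a separate secondary endpoint and is where reduced dosing would appear. In the constant-benefit model the number of doses, a proxy for opioid use, has 78/81/82% power with 2-point analgesia, more than fixed pain scores have. So the plan is not blind to a home benefit. But opioid use does not correct the pain comparison, which the plan lists in its own right.

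Fourth, fixed scores are no cure-all. Dose-linked scores have more power in three of the six settings above. With a waning benefit, fixed scores have only about 14–16% power, and diary entries may not be missing at random. All of this stands, so the case for fixed scores is interpretability. Scores before and after a dose can also describe response to medication, which is a reason to keep them as descriptive data.

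**Conclusion.** The concern holds in a limited form. As written, the home part of the secondary pain endpoint compares patients and moments selected after randomisation. That follows from the text alone.

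The size is illustrative. With as-needed dosing, a constant benefit similar across patients and 2-point analgesia, dose-linked scores show 0.37 to 0.50 where observed pain differs by 0.65 to 0.67. With 3-point analgesia the shortfall is 0.10 to 0.18. The sign can reverse if only patients with milder pain benefit, and scheduled dosing largely removes the selection. No direction or size can be fixed from the documents.

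A reader might go further and infer that the trial's main conclusion is at risk. It is not: the four-hour opioid endpoint and the clock-timed PACU pain scores do not depend on home dosing. This is a cheap improvement worth making to one component of one secondary endpoint, not a flaw in the trial's core.

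**What to change.** In 9.h.2, ask every patient also to record pain at a few pre-set clock times to the end of postoperative day one, whether or not medication was taken. Spread the times so that some fall in the early hours after discharge, where a single-shot block is most likely to show an effect.

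In 9.i.4, name the per-patient mean of those scores as the post-discharge pain endpoint, compared by ANCOVA with surgery type and read alongside opioid use to day one. Fixed scores measure pain with medication use included, so neither endpoint tells the whole story alone. Keep the dose-linked scores as descriptive, and report per arm how many patients had none.

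The cost is about four extra entries on a record patients already keep, and a sentence in each of the two sections. Treatment, visits and staffing do not change. Some entries will be missed: in the constant-benefit model, 10% missing at random leaves the difference unchanged and lowers power by about 1 to 3 percentage points, which may be optimistic for a home diary. Power may be lower than with dose-linked scores in some settings, and a short-lived benefit would still be understated. The gain is a home pain comparison intended for all randomised patients and free of selection by dosing.

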SERRATUS PLANE BLOCK FOR POST-OPERATIVE PAIN CONTROL IN BREAST SURGERY

A Randomized, Double Blind, Placebo-controlled Study at Long Island Jewish Medical Center
and Center for Advanced Medicine

Principal Investigator: [name]
Anesthesiology
Long Island Jewish Medical Center
[name],
[name]

Funding Sponsor: Not Applicable

Study Product: Bupivacaine HCl

Protocol Number: 15-246

IND/IDE Number: IND Exempt

LIST OF ABBREVIATIONS

AE	Adverse event
cm	Centimeter
DSMB	Data Safety Monitoring Board
FDA	Food and Drug Administration
ID	Identification
IRB	Institutional Review Board
IV	Intravenous
kg	Kilogram
m	Meter
ME	Morphine equivalents
mg	Milligram
mL	Milliliter
MME	Morphine Milligram Equivalent
NSAID	Non-steroidal anti-inflammatory drugs
PACU	Post-anesthesia care unit
PCA	Patient-controlled analgesia
PHI	Protected health information
PI	Principal investigator

CONFIDENTIAL

This document is confidential and the property of Northwell Health. No part of it may be transmitted, reproduced, published, or used by other persons without prior written authorization from the study sponsor.

STUDY SUMMARY

Title	SERRATUS PLANE BLOCK FOR POST-OPERATIVE PAIN CONTROL IN OUTPATIENT BREAST SURGERY
Short Title	Serratus Plane Block
Protocol Number	15-246
Phase	4
Methodology	Double-blind, Randomized, Placebo Control Design
Study Duration	18 Months
Study Center(s)	Single-center
Objectives	Efficacy of Serratus Plane Block for postoperative pain management after breast surgery. Determine if use provides superior pain control to standard of care, as evidenced by decreased opioid consumption. Secondary objectives include assessments of pain, incidence and severity of opioid related adverse events including postoperative nausea and vomiting at regular time intervals, antiemetic use and overall patient experience and satisfaction.
Number of Subjects	90
Diagnosis and Main Inclusion Criteria	Breast Surgery
Study Product, Dose, Route, Regimen	Bupivacaine HCL, 20mL bolus of drug or placebo, 0.25% of bupivacaine.HCl or 0.9% saline, respectively will be administered underneath the fascia of the serratus muscle using ultrasound guidance.
Duration of administration	Single bolus before surgery
Reference therapy	Placebo
Statistical Methodology	Analysis of covariance (ANCOVA) with “type of surgery” as a covariate will be used to compare mean ME between the two groups.

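### Does the primary opioid analysis need a fixed rule for when to log-transform and how to treat patients with 0 ME?

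*Combined protocol and SAP*

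**What the plan says.** The Study Summary and section 9.i.4 give the primary method as ANCOVA, with type of surgery "as a covariate will be used to compare mean ME between the two groups". Section 9.i.4 then adds: "Data transformation (presumably a log transform) will be considered in order to achieve the required assumptions of normality and equal variance". The Study Summary leaves that sentence out, which is ordinary abbreviation and not a conflict.

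Three other places bear on the point.

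- **Zeros are possible.** Section 9.h.1 says that "oral and IV rescue medication will be administered to both groups upon request as per standard of care". Item 3 of sections 9.e and 9.f says: "Patients will receive oral standard post-operative pain and nausea management on an as-needed basis in the PACU". Section 9.g, item 17, lists non-opioids beside the opioids: "Postoperative oral administration (including total dose) of Percocet, morphine, dilaudid, Tylenol, Toradol, and other analgesic agents". A patient who asks for no opioid in the first 4 hours has 0 ME.
- **Every patient counts.** Section 9.i.5: "The ITT population will be defined as all subjects who are randomized". The primary analysis uses that population.
- **The planning values are on the untransformed scale.** Section 9.i.6: "it is expected that the Placebo group will average 12 ME (SD=4) of narcotics in the PACU", and "A reduction of 20% to 9.6 ME in the Bipuvacaine group would be clinically significant". The target is thus given both as a difference and as a percentage.

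**The concern.** The log of zero does not exist. If the presumed log is used and one patient has 0 ME, the analyst must either drop her, against section 9.i.5, or add a constant that the plan does not name. The block is meant to reduce opioid need, so patients with 0 ME may be its best outcomes, and they are the ones without a rule.

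The plan also does not say which diagnostic prompts the transform or whether the choice comes before unblinding. Untransformed ME, log(ME+1), log(ME+0.1) and log with zeros dropped can give different p-values. If the version were chosen after seeing results by arm, the type I error of the trial's single primary test would exceed 5%. The effect measure would also move from a difference in means to a ratio.

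**Working it through.** **1. The plan's own figure.** Inputs from section 9.i.6: means 12 and 9.6, SD 4, 45 per arm, two-sided alpha 0.05. The noncentrality is 2.4 / (4 × √(2/45)) = 2.4 / 0.843 = 2.85 on 88 degrees of freedom. Power is 80.4%, and 45 is the smallest number per arm that reaches 80%. The stated sample size reproduces on the untransformed scale.

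**2. How many zeros to expect.** The documents give no rate. Taking the planning normal model and reading values at or below 0 as 0 ME:

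- placebo: Φ(−12/4) = Φ(−3) = 0.00135
- block: Φ(−9.6/4) = Φ(−2.4) = 0.00820
- expected number: 45 × 0.00135 + 45 × 0.00820 = 0.43 patients
- chance of at least one: 1 − 0.99865^45 × 0.99180^45 = 0.35

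Assumed shares of 1%, 2% and 5% in both arms give 1 − 0.99^90 = 60%, 1 − 0.98^90 = 84% and 1 − 0.95^90 = 99%. A zero is plausible; how many is unknown.

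**3. An analyst who follows the stated purpose.** Simulation with 10,000 trials per scenario, 45 per arm, and ANCOVA with three surgery types (15 per arm in each). ME among opioid users is log-normal. Arm means and SD, zeros included, are held at 12, 9.6 and 4. This analyst takes the log only if Shapiro-Wilk rejects normality of the untransformed residuals and log(ME+1) fits better.

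| Zeros per arm (assumed) | Power, untransformed | Power, purpose-following | Log used | Type I error, purpose-following |
|---|---|---|---|---|
| 0% | 80.3% | 89.4% | 90% | 4.9% |
| 1% | 79.8% | 83.0% | 37% | 5.0% |
| 2% | 79.6% | 80.8% | 14% | 5.1% |
| 5% | 79.2% | 79.3% | 1% | 5.6% |

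As zeros become more common the log fits worse, so the fit check steers away from it. At 2% zeros with other shapes, untransformed and purpose-following power are 78.5% and 78.5% (near-normal users) and 79.5% and 80.1% (gamma users). Under the planning normal model cut at 0, both are 79.8%. Two such analysts using constants 1 and 0.1 disagree on significance in at most 0.4% of trials at the planning values.

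**4. Where the large figures come from.** At 2% zeros with log-normal users, a log used whatever its fit has 65% power with constant 1 and 44% with constant 0.1, and the two disagree in 21% of trials. Log(ME+1) and dropping zeros disagree in 30%. Under the planning normal model these disagreements fall to 4% and 7%.

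**5. Choosing the smallest p-value.** Across zero shares of 0 to 5%, the smallest p of untransformed, log(ME+1) and log(ME+0.1) gives type I error of 5.5 to 7.6%. The upper limit reaches 10.6% only if dropping zeros is added as a fourth choice.

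**6. What a fixed rule would buy.** Take a rule that allows the log only if nobody has 0 ME and blinded pooled residuals look non-normal. Its power at 0/1/2/5% zeros is 89.1/82.7/80.7/79.2%, in effect the same as the table. Outside the planning SD (users' coefficient of variation 0.8, 30% reduction), two sets of runs give:

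- zeros 0% placebo, 3% block: rule 64 to 66%, purpose-following 76 to 79%
- zeros 10% in each arm: rule 45 to 48%, purpose-following 36 to 37%

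Staying untransformed in every case is simpler, but gives up the gain from 80% to 89% when there are no zeros and ME is log-normal.

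**The case for a change.** The best argument for a change is that it costs only wording. Naming a purpose is not the same as naming a rule. The plan cannot show afterwards which version of its one primary test was fixed in advance. Section 5.h also says that the Biostatistics Unit contact who generates the randomization numbers is unblinded, so the plan alone does not guarantee a blinded choice. There are also skewed settings in which even the purpose-following analyst does worse than the untransformed analysis. With a coefficient of variation of 0.8, a 40% reduction and 10% zeros, power is 61% with constant 1 or 68% with constant 0.1, against 76%, and the two constants disagree in 20% of trials.

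What stands is that the detail is missing and that the choice of version is open. What does not stand is the step from there to a flaw in the plan. The 65%, 44% and 21% need a log applied without regard to fit, although section 9.i.4 allows one only to meet the model's assumptions. The 30% and the 10.6% need patients dropped against section 9.i.5. The skewed case lies well outside the plan's SD of 4 on a mean of 12. The rule in step 6 has faults of its own: one patient with 0 ME switches the effect measure, and pooled residuals without treatment cannot check equal variance between arms, which is half of the stated aim.

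**Conclusion.** No change follows. This is a gap that an analyst fills sensibly: the default is ANCOVA of untransformed ME on everyone randomized, where 0 is an ordinary value, and a transform comes in only where it improves the fit. Followed that way, the plan keeps or exceeds its 80% power to within a point at the planning values, with type I error of 4.9 to 5.6%. The remaining risk is selection after the fact among versions that keep all patients, worth 0.5 to 2.6 points of type I error above 5%.

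The alternatives are trade-offs. One matches the purpose-following analyst at the planning values and wins or loses elsewhere; the other surrenders up to 9 points of power when there are no zeros.

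The conclusion rests on assumed zero shares of 0 to 5%, on the planning means and SD, and on an analyst who checks normality. The simulated analyst did not check equal variance. Zero shares near 10% with a much larger SD would make the choice of scale matter more, but the documents give no sign of such data.
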